8. ETHICAL CONSIDERATIONS

8.1 Regulation statement

The study will be conducted according to the principles of the Declaration of Helsinki (Fortaleza, Brazilian amendment, October 20013) and in accordance with the Medical Research Involving Human Subjects Act (WMO) and other guidelines, regulations and Acts.

8.2 Recruitment and consent

An information letter will be sent to the participants of AMS-OA cohort by the study investigator with the request to participate the study. Participants will be given two weeks to respond to the letter if they are interested in participating using the reply form to state their intentions. If no response is received after this time, a follow up letter will be sent to offer patients the opportunity to take part in the study. An investigator from the research team will inform subjects about the study and seek consent from the subject. Informed consent will be obtained from each subject, after the information letter has been provided. The study investigator will make sure that the volunteers are given complete, adequate, written and oral information regarding the nature, aims, possible risks and benefits of the study. It will be explained to the volunteers that they are free to interrupt their participation in the study at any moment without any consequence. The volunteers must keep a copy of the information sheet and informed consent form.

8.3 Benefits and risks assessment, group relatedness

The application of gait modifications and walking on a treadmill has no known side effects. Subjects will wear a safety harness while walking on the treadmill. Periods of rest will be allowed during the measurements to prevent fatigue. (see also risk analysis, appendix B2).

Although there may not be a direct benefit to the subjects in Study A, specifically those who do not go on to Study B, it is anticipated that these patients may benefit through obtaining more knowledge on their own gait pattern. For subjects in Study B, it is anticipated that they will benefit through modification to their gait pattern, resulting in a reduction of pain.

8.5 Incentives (if applicable)

There are no special incentives, compensation or treatment for the participants. Participants will receive reimbursement for their travel expenses.

9. ADMINISTRATIVE ASPECTS, MONITORING AND PUBLICATION

9.1 Handling and storage of data and documents

The data of each subject will be stored in a case record form (CRF, patient data file) and in a computer file for analysis. Subjects will be anonymous as each participant will be identified in the database by a specific study number. The code is filed separately and will be available to the participating investigators for the duration of the study only. The CRF is available to the investigators and the subject involved and will not be disclosed to a third party. The subjects will be informed in writing about these data storing and handling procedures, with a clear statement that discretion will be guaranteed. The administration of the study will be performed by the study investigators.

9.2 Monitoring and Quality Assurance

An independent monitor (quality officer) will monitor the study data according to Good Clinical Practice (GCP). A selection of the test subjects Informed Consents forms will be checked. Additionally, during the onsite monitoring Source Data verification will be performed to ensure that data in the Case Report Forms (research forms / questionnaires) match the source data (patient records, lab results, etc.). The intensity of this verification is related to the risk of the study. data will be monitored in any event, the inclusion and exclusion criteria and the primary outcomes of the study. The monitor will also look at whether all (S) AEs and SUSARs are adequately reported within the timelines as required by law - and regulations.

Data storage and methodological procedures will be monitored annually by the Clinical Research Bureau. All files will be made available for audits as required by the Clinical Research Bureau.

9.3 Amendments

Amendments are changes made to the research after a favourable opinion by the accredited METC has been given. All amendments will be notified to the METC that gave a favourable opinion.

9.4 Annual progress report

The sponsor/investigator will submit a summary of the progress of the trial to the accredited METC once a year. Information will be provided on the date of inclusion of the first subject, numbers of subjects included and numbers of subjects that have completed the trial, serious adverse events/ serious adverse reactions, other problems, and amendments.

9.5 End of study report

The investigator will notify the accredited METC of the end of the study within a period of 8 weeks. The end of the study is defined as the last patient's last visit.

In case the study is ended prematurely, the investigator will notify the accredited METC within 15 days, including the reasons for the premature termination.

Within one year after the end of the study, the investigator/sponsor will submit a final study report with the results of the study, including any publications/abstracts of the study, to the accredited METC.

9.6 Public disclosure and publication policy

There are no conflicts of interest. There are no specific arrangements made between the sponsor and the investigator concerning the public disclosure. All members of the project team will be involved as co-authors in publications.

10. PLANNING

The total project will take 3 years (36 months) from September 2015 to February 2018.

| Month 1-3: | Start of project, training assessments |
|--------------|--|
| Month 4-20: | Patient inclusion period |
| Month 21-25: | Data analysis |
| Month 26-35: | Report on effectiveness |
| Month 36: | End of project |

13. APPENDIX A1

The below decision tree is proposed to help the researcher and clinician determine the appropriate feedback instructions for the individual patient based on a) their baseline measures b) their measures during the implicit learning phase (where no instruction will be provided) and c) a priori knowledge (see Table 1). In this way we hope that the subjectivity is removed. Clear instruction will be provided to the patient to ensure that they are aware of how their movements are represented in the on-screen feedback.

If the patient reports pain or discomfort during any of the modifications, then the specific modification thought to be associated with the increased pain level, will be contraindicated for the specific patient. Indications of pain will be recorded on the case record form.

Abbreviations used in the table are explained below.

FPA – foot progression angle, for the purposes of the below table a foot progression angle of greater than 0 (FPA>0) refers to an internally rotated FPA and a foot progression angle of less than 0 (FPA<0) refers to an externally rotated FPA.

KAM- knee adduction moment

KF- knee flexion (referring specifically to the stance phase knee flexion; i.e. during weight bearing.)

SW- step width

TS- trunk sway (note this is included as a variable to monitor, but it will not be used as a variable that is fed back to the patients in order to reduce KAM).

MKT – medial knee thrust. Since we cannot measure knee adduction angle in real time, feedback of this should be the position of the lateral knee marker with respect to the centre of mass in the frontal plane.

Subscript baseline and implicit refer to the data collected in the baseline phase or implicit learning phase.

Subscript patient refers to the average step width in both the baseline and implicit learning phase.

Subscript references refers to normal step width (note this is from healthy individuals walking on the treadmill, but may not be aged matched to the population in this study).

| Gait | IF | AND | AND | THEN | INSTRUCTION TO | INSTRUCTION TO | FEEDBACK EXAMPLE |
|--------------|--------------------------------|----------------------------|----------------------------|----------------------|---------------------------|-------------------------|--|
| modification | | | | | PATIENT (internal | PATIENT (external | (S) |
| | | | | | focus of attention) | focus of attention) | |
| Foot | FPA _{baseline} < | KAM _{implicit} < | FPA _{baseline} - | Modification of | Rotate your foot | Keep the marker on | 1) Target FPA shown by |
| Progression | FPA _{implicit} | KAM _{baseline} | $FPA_{implicit} \lesssim$ | FPA considered | more towards the | your big toe pointing | onto treadmill and |
| Angle | | | ±15 | appropriate for this | centre of the | further towards the | screen with sound |
| | | | | patient. | treadmill. | centre of the treadmill | effect/ visual reward when target angle is |
| | FPA _{baseline} > | KAM _{implicit} < | FPA _{baseline} - | | Rotate your foot | Keep the marker on | matched- Knowledge |
| | FPA _{implicit} | KAM _{baseline} | $FPA_{implicit} \lesssim$ | | more towards the | your big toe pointing | of results |
| | | | ±15 | | centre of the | further towards the | progression angle, |
| | | | | | treadmill. | centre of the treadmill | depicted by a graph |
| | | | | | | | with target area shaded- Knowledge |
| | | | | | | | of performance |
| | | | | | | | |
| Step width | SW _{baseline} < | KAM _{implicit} < | | Modification of step | Increase your step | Increase the distance | 1) Target step width |
| | SW _{implicit} | KAM _{baseline} | | width considered | width | between the centre of | projected onto |
| | | | | appropriate for this | | the treadmill and the | treadmill and screen |
| | | | | patient | | marker on your big | with sound effect/ visual reward when |
| | SW _{baseline} ≈ | SW _{patient} < | KAM _{reference} < | | | toe | target angle is |
| | SW _{implicit} | SW _{reference} | KAM _{patient} | | | | matched- Knowledge |
| | | | | | | | 2) Step width depicted |
| | | | | | | | by a graph with |
| | | | | | | | target area shaded |
| | | | | | | | performance |
| Medial knee | MKT _{baseline} < | KF _{baseline} ≤ | Patient not | Modification of the | When you take the | When you take the | 1) Graph showing |
| thrust | MKT _{implicit} | KF _{implicit} ≥ 0 | reporting | medial knee thrust | weight onto your | weight onto your 'left/ | on knee in frontal plane |
| | | | discomfort in | considered | 'left/ right' leg, try to | right' leg, try to bend | during stance phase |

| Gait modification | IF | AND | AND | THEN | INSTRUCTION TO PATIENT (internal | INSTRUCTION TO PATIENT (external | FEEDBACK EXAMPLE (S) |
|----------------------|--|-----|----------|--|---|---|---|
| | | | | | focus of attention) | focus of attention) | |
| | | | the knee | appropriate for this patient | bend your knee and move your knee towards the centre of your body. | your knee and move the marker on your knee towards the centre of your body | with target region – knowledge of performance 2) Target value for medial knee thrust based on MTK _{implicit} shown, with reward when target is reached- knowledge of results |
| Trunk lean/ sway | TS _{implicit} ≫ TS _{baseline} | | | Trunk sway being used excessively to control KAM | Reduce trunk sway | | No feedback given |

| | | Study | Study B | | | | |
|-----------------------|---|-------|---------|----|----|--------------|--|
| | A | | | 1 | | 1 | |
| | | M1 | M1 | M2 | М3 | M4 | |
| | Consent | ✓ | | | | | |
| | Basic demographics | ✓ | | | | | |
| | WOMAC | ✓ | ✓ | ✓ | ✓ | ✓ | |
| | NRS pain over last week | ✓ | ✓ | ✓ | ✓ | ✓ | |
| | Knee instability | ✓ | | | ✓ | ✓ | |
| | Knee confidence | ✓ | | | ✓ | ✓ | |
| | | | | | | | |
| Questionnaires | NRS pain during walking on treadmill | ✓ | 1 | ✓ | ✓ | ✓ | |
| | Feedback on feedback | ✓ | | | | | |
| | Satisfaction with the program | | | | | | |
| | Compliance with the modified | | | ✓ | ✓ | ✓ | |
| | gait pattern | | | | | | |
| | Timed GUG | ✓ | ✓ | | ✓ | \checkmark | |
| | 10m walk test (fast) | ✓ | ✓ | | ✓ | ✓ | |
| Activity/ performance | 10m walk test (comfortable) | ✓ | ✓ | | ✓ | ✓ | |
| lesis | Muscle strength | ✓ | ✓ | | ✓ | ✓ | |
| | | | | | | | |
| | Baseline own shoes | ✓ | ✓ | ✓ | ✓ | ✓ | |
| | | | | | | | |
| | Implicit learning | ✓ | | | | | |
| | Explicit learning 1 | ✓ | | | | | |
| | Explicit learning 2 | ✓ | | | | | |
| Gait and balance | Explicit learning 3 | ✓ | | | | | |
| | Training | | ✓ | ✓ | | | |
| | Retention | ✓ | ✓ | ✓ | | | |
| | Dual tasking- cognitive | | ✓ | ✓ | ✓ | \checkmark | |
| | Dual tasking- physical | | ✓ | ✓ | ✓ | \checkmark | |
| | | | | | | | |

14. APPENDIX A2: Patient measurements at each stage of the patient journey

| Study B | | | | | | | | |
|---------|-----------|----|----|------------|-----|--|--|--|
| T1/ | T2 | Т3 | Τ4 | T 5 | T6/ | | | |

| | M1 | | | | | M2 |
|--|----|---|---|---|---|----|
| NRS pain during last week | ✓ | ✓ | ✓ | ✓ | ✓ | ✓ |
| NRS pain during walking on treadmill | ✓ | ✓ | ✓ | ✓ | ✓ | ✓ |
| Activity levels over last week- step counter | ✓ | ✓ | ✓ | ✓ | ✓ | ✓ |
| | | | | | | |
| Difficulty and "normalness" of learned walking | ✓ | ✓ | ✓ | ✓ | ✓ | ✓ |
| pattern | | | | | | |
| Compliance with modifications over the last week | ✓ | ✓ | ✓ | ✓ | ✓ | ✓ |

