the various gait modification conditions (study A: 1. baseline; 2. KAM feedback without kinematic instructions, audio and visual feedback; 3. Kinematic feedback without further instructions (toe-out or -in, step width and medial thrust); 4. KAM feedback with additional verbal kinematic instructions about an effective gait pattern that can be sustained in daily life: 5. maintaining the pattern from 4. without any feedback) and during and after the training sessions (study B: 1. baseline; 2. try to replicate the pattern learned in study A without feedback; 3. KAM feedback with kinematic instructions from study A; 4. maintaining the pattern from 3. without feedback; follow-up after 3 and 6 months). Linear mixed models will be used to calculate statistical differences. Secondary parameters will include external knee flexion moment (KFM), and kinematic pattern (joint angles and temporal-spatial parameters) as measured by the GRAIL; pain as measured by the numeric rating scale and will be assessed during the different gait modification patterns (as for the KAM).

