| Condition | Description | Time (minutes) | Purpose | Recording time (seconds) |
|-----------|--------------------|----------------|----------------------|-----------------------------|
| 0 | Acclimatization to | 3 (max) | To determine the | 0 |
| | treadmill | | average (mean) speed | |
| | | | of walking of the | |

The following protocol will be used in Study A:

| Condition | Description Time (minutes) Purpose | | Purpose | Recording time |
|-----------|---|--|--|--|
| | | | | (seconds) |
| | | | patient for use in further trials. | |
| 1 | Baseline condition- own shoes | 2 | 30 seconds familiarization plus 90 seconds recording time | 90 |
| 2 | Baseline condition- standard shoes | 2 | 30 seconds familiarization plus 90 seconds recording time | 90 |
| 3i | Implicit learning phase- standard shoes with real time visual feedback on KAM | 2 | 30 seconds familiarization plus 90 seconds recording | 90 |
| 3ii | Implicit learning phase- standard shoes with real time audio feedback on KAM | 2 | 30 seconds familiarization plus 90 seconds recording | 90 |
| | | | | |
| 4 | Training phase with explicit instructions | 3 x 2 mins | Feedback on up to 3 kinematic parameters separately 30 seconds familiarisation plus 90 seconds recording | 270 |
| 5 | Measurement- new pattern with feedback | 2 | Measurement of pattern with direct KAM feedback (30 seconds familiarization and 90 seconds recording) | 90 |
| 6 | Measurement- new pattern | 2 | Measurement of pattern without any feedback (30 seconds familiarization and 90 seconds recording) | 90 |
| | | Total walking time: 19.0 minutes maximum (N.B. Regular breaks can be taken as necessary to prevent fatigue). | | Total recording time: 720 seconds =12.0 minutes in 8 individual recordings. |

In stage 3 of the assessment, the subject will be instructed to decrease the KAM. The subjects will therefore apply an individual kinematic strategy to reach this goal [8;43]. Feedback will provide the subject with knowledge of result but not knowledge of performance

so it will up to the individual to devise their own strategy. At this stage no further instructions will be given about kinematic strategies or compensations. This will allow measurement of the implicit motor learning using an external focus of attention [58].

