In step 4, explicit verbal instructions will be given on the gait pattern in addition to the realtime visual KAM feedback to further develop a pattern that can be sustained in daily life (e.g. toe-in/out <15deg). Hunt and Takacs (2014) mentioned that a toe-out position of \pm >15 (difference from baseline) is difficult to obtain [3]. Reference values of step width and medial thrust/ frontal plane position of the knee, will be obtained from the baseline trial and the initial trials with feedback on the KAM. This will enable threshold limits to be set such that the step width (for example) is not increased to an excessive degree. The values of all of the kinematic and kinetics will be available for the researcher in real time. In this way, the instructions to the patient can be adapted to suit the individual patient, based on objective information. In step 6, the optimal gait pattern will maintained by the subject without any feedback.

| Condition | Description | Time | Purpose | Recording |
|-----------|--|---|--|-----------|
| | | | | time |
| | | | | (seconds) |
| 0 | Acclimatization to treadmill | Up to 4 minutes | To determine the average (mean) speed of walking for use in training period | 0 |
| 1 | Baseline condition- own shoes | 60 seconds minutes | 15 seconds familiarization plus45 seconds recording time | 45 |
| 2 | Training phase | Up to 21 minutes depending on the week | This will be based on the results of study A. Explicit guidance will be given as required. Frequency of the feedback will be adjusted if necessary to avoid dependence on it and encourage motor learning. | 0 |
| 3 | Measurement without feedback while new pattern is applied | 60 seconds | 15 seconds familiarization plus 45 seconds recording time | 45 |
| 4i* | Measurement without feedback, -with dual tasking (Stroop test/ memory test) | 75 seconds | 30 seconds familiarization plus 45 seconds recording | 45 |
| | • | | | |

The following protocol will be used in Study B for each of the two sub-groups.:

| 5 | Advice for home | ~8 minutes | Clinician/ physio to offer advice | 0 |
|---|-----------------|------------|-----------------------------------|---|
| | training | | for home training | |

Steps 0,1,2,3 and 5 repeated at weekly intervals.

* Steps 4i, 4ii and 5 will only be applied during week 4 to 6, thus the time taken for training sessions 1 to 3 will be shorter.

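### In the Appendix A1 decision tree, the foot-progression-angle row triggered by outward rotation gives a toe-in instruction, and no row gives a toe-out instruction.

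*Protocol*

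**What the plan says.** The abbreviations in Protocol section 13 (Appendix A1) fix the sign convention: an FPA above zero "refers to an internally rotated FPA and a foot progression angle of" less than zero is externally rotated.

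The decision tree then has two FPA rows. Both require a lower KAM in the implicit learning phase than at baseline and a change in FPA within about 15 degrees. They differ in the direction of the FPA change.

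- The first row requires baseline FPA below implicit-phase FPA. Its instruction cells continue "centre of the | further towards the | screen with sound".
- The second row requires baseline FPA above implicit-phase FPA: "FPA _{baseline} > | KAM _{implicit} < | FPA _{baseline} - | | Rotate your foot | Keep the marker on". Its instruction cells continue "centre of the | further towards the | progression angle".

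(In each quote the last fragment after a bar, where it concerns sound or a graph, belongs to the neighbouring feedback-example column.)

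Elsewhere the protocol plans for both directions. The Summary lists "Kinematic feedback without further instructions (toe-out or -in, step width and medial thrust", and step 4 in section 5.2 aims for "a pattern that can be sustained in daily life (e.g. toe-in/out <15deg". Table 1 in section 1 gives toe-out its own entry.

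**The concern.** The tree links what a patient did spontaneously in the implicit phase to the explicit instruction given next. A patient who rotated the foot outward while KAM fell should be told to do more of that. The second FPA row tells the patient to rotate inward instead.

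Explicit instruction is part of the primary objective of Study A (section 2), and training in Study B is based on the results of Study A (section 5.2). The two directions are not interchangeable. Table 1 ties toe-in mainly to the first KAM peak and toe-out to the second, and section 7.1 extracts both peaks as outcomes. A reversed cue could therefore change which peak is affected. Appendix A1 also states the hope that the tree takes subjectivity out of the choice. For second-row patients, staff must either follow it and give the opposite cue or override it by judgement, which defeats that purpose.

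**Working it through.** There is no planned figure to reproduce. The check compares signs row by row, and recording times then give the scale.

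**Direction.** Positive FPA is toe-in, so a rise in FPA is inward rotation and a fall is outward rotation. The angles below are assumed, for illustration only.

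| | First FPA row | Second FPA row |
|---|---|---|
| Trigger | baseline < implicit, KAM lower | baseline > implicit, KAM lower |
| Example (degrees) | −5 to +2 | −5 to −12 |
| Change (implicit − baseline) | +2 − (−5) = +7, inward | −12 − (−5) = −7, outward |
| Within 15 degrees? | yes | yes |
| Printed cue | foot and toe marker towards the midline (FPA rises) | the same (FPA rises) |
| Agrees with trigger? | yes | no |

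**Could another row supply toe-out?** No.
- The step-width row asks for more distance between the toe marker and the midline, which concerns foot placement and not foot angle.
- The medial-thrust row concerns bending the knee and moving it inward.
- The trunk row asks for less sway.
- The FPA feedback examples (a target angle, a shaded graph) name no direction, and the 15-degree limit does not set one.

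**Could it be an artefact of reading the table from PDF?** This is unlikely. Cells shared between rows are not repeated in this table: the THEN cell is blank in the second FPA row, and the second step-width row has no instruction text of its own. The second FPA row prints a complete instruction in both columns. A copy of the first row is the more likely cause.

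**Exposure per affected patient.** Recording times are from the Study A table in section 5.2. Condition 4 is described as "Feedback on up to 3 kinematic parameters separately".
- Conditions 4, 5 and 6: 270 + 90 + 90 = 450 s.
- The FPA trial is one of three in condition 4: 270 / 3 = 90 s, and 90 / 450 = 20%.
- If FPA is also the pattern carried into conditions 5 and 6: 90 + 90 + 90 = 270 s, and 270 / 450 = 60%.

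These are shares of recording time, not sizes of error in KAM.

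**How many patients.** The documents do not say. The nearest count is in Table 1: 14 of 16 healthy subjects, given suggestions, chose toe-in. At most 16 − 14 = 2 of 16 (12.5%) can have chosen toe-out. If that share held here, it would be 0 to 0.125 × 41 = 5.1, or about 0 to 5 patients. That is an assumption and not a bound. The healthy subjects had suggestions, the other two are not reported as toe-out, and the row is triggered by any outward change with any fall in KAM.

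**The case against.** The strongest reply is that this is a copying slip in an aid and not a binding rule. Appendix A1 proposes the tree as help for the researcher and clinician, and it names Table 1, where toe-out is described, as one of its inputs. Staff must first see that the foot turned outward before they reach the second row, so the mismatch is visible when the row is used. Section 5.2 gives the researcher all kinematic and kinetic values in real time and says that "the instructions to the patient can be adapted to suit the individual patient, based on objective information". A cue that failed to lower KAM would be an unlikely choice for conditions 5 and 6, since the carried pattern is meant to be effective. The patient count rests on a different population and task. The reader program also garbled words elsewhere in the protocol's tables, so the source page deserves a look.

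Much of this stands as a limit on size. The 60% is a ceiling, the count of 0 to 5 is only an illustration, and checking the source page before re-issue is sensible. None of it reconciles the row with its trigger. Discretion to depart from a wrong standard instruction is no reason to leave it in place.

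**Conclusion.** The second FPA row of Appendix A1 is wrong as written. Under the appendix's own sign convention its instruction is opposite to its trigger, and the tree has no toe-out instruction although the protocol plans for that modification. This conclusion rests on the printed table and needs no numerical assumption.

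The consequence is limited and its frequency is unknown. It concerns patients who lowered KAM with outward rotation, and for them one of up to three separately trained parameters, with more of the recording involved only if FPA is the pattern carried forward. The lower KAM merely accompanied the outward rotation, so harm from a toe-in cue is not shown. Loss of Study B entrants is possible but also not shown: section 4.2 leaves the 10% KAM criterion to the clinicians' discretion and does not name the condition in which it is judged. Sample size and the planned analysis are unaffected. It should be fixed because the error is clear and the correction is nearly free.

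**What to change.** In the second FPA row, reverse both instruction cells. The internal-focus cell should tell the patient to turn the foot further away from the midline of the treadmill. The external-focus cell should tell the patient to point the big-toe marker further away from it. The clinical team should settle the final wording. Re-issue Appendix A1 and notify the staff who use it.

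Recording on the case record form which row and instruction were used is optional. No dedicated sensitivity analysis is needed. The cost is two table cells and a notice to staff.
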